#### **Process Data**

Brief interviews with participants after each session. After each intervention and control session, all couples will complete a brief semi-structured interview (~5 min) to assess acceptability of the intervention content and structure, rating perceived importance and satisfaction with intervention content, and an open-ended question on what they liked and disliked. These brief semi-structured interviews will also include questions to assess any unanticipated negative adverse events occurring because of the intervention (e.g., partner conflict).

**Exit interviews with participants post-intervention**. Within 3-4 weeks of the pilot intervention, brief semi-structured exit interviews (~15 min) will be conducted with intervention participants (n=70), as well with facilitators (n=2), participating health workers (n=2), and community leaders (n~2-4) to further assess acceptability, feasibility, appropriateness, barriers to implementation/utilization, areas for improvement, and progress on "Family/Community Action Plans." Exit interviews can be conducted in-person or over the phone. See Table 3 for more detail on measures of acceptability and feasibility for intervention content and structure.

**Data collection to assess intervention fidelity.** Facilitators will follow a fidelity checklist to ensure all steps are completed, which will also be monitored in early dialogues and then randomly throughout the course of the study through direct observation of intervention sessions by research

staff to allow for immediate feedback. Staff will complete a session checklist on activities conducted, number of participants, engagement, and issues encountered including those related to community leader participation (providing immediate feedback to ensure fidelity). In addition, a randomly selected portion (~20%) of the dialogues will be audio recorded, transcribed, and analyzed for fidelity.

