### Women found pregnant at baseline

If pregnant, the research assistant will inform the woman of the test results alone, unless the woman prefers for them to be delivered with her husband present. The research assistant will then provide brief couples counseling on the importance of prenatal care, having a skilled attendant at birth, and breastfeeding, provide an information sheet with a list of nearby health facilities offering free prenatal care, and a paper referral to the couples' preferred health facility. She and her partner will be withdrawn from the study and informed of their withdrawal.

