## Data safety monitoring plan

The proposed study will conform to rigorous monitoring procedures, standardized reporting of adverse events using Event Report Forms, regular review of the study by the joint-Principal Investigators (PIs), Drs. [name] and [name], and review of the study by a Data and Safety Monitoring Board (DSMB).

The PIs, Drs. [name] and [name], [name], and research staff, will ensure appropriate: (1) conduct of the informed consent process (e.g., that informed consent is obtained before proceeding with study procedures and properly stored), (2) enrollment of study subjects, (3) collection and analysis of data, (4) implementation of study procedures to ensure consistent monitoring of subjects for possible adverse events, (5) review of adverse events and reporting to the DSMB and IRB, and (6) maintenance of the privacy and confidentiality of study subjects. The PIs maintain ultimate responsibility for the project and for the safety of study participants.

[name] and [name] will be responsible for meeting with the research team on a regular basis (weekly, either in person or by conference call) to review the progress of the study and address any human subject issues that occur. These discussions may involve adverse event prevention measures, recruiting of appropriate study subjects, research staff training on protection of human subjects, as well as occurrence of adverse events, unexpected incidents, or protocol problems. The joint-PIs and subcontract PI will meet with the research assistants regularly to go over the progress of the study and communicate any issues or adverse events to the joint-PIs. [name] will compile reports on this information to submit to the PIs and Data and Safety Monitoring Board (DSMB) for review.

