## Monitoring Intimate Partner Violence (IPV)

Though we expect the risk of adverse events resulting from participation in the intervention to be low, since we are working with couples and facilitating discussions around sensitive topics, such as family planning and gender norms, we have developed procedures to closely monitor participants in the couples' intervention. The implementation of these procedures will ensure any unanticipated adverse events related to violence or relationship conflict are identified and addressed immediately. First, our baseline data will assess participants' history of experiencing and perpetrating intimate partner violence. We will use this data to identify couples who report a history of violence, so that intervention facilitators can closely monitor those couples, and pay special attention to issues of violence in the intervention sessions to minimize the risk of conflict arising between couples. In addition, after each couples' session, men and women will separately complete a brief questionnaire to collect process data on the feasibility and acceptability of the intervention. In addition to questions on feasibility and acceptability, this questionnaire will include questions to assess if the intervention had any negative consequences on couples' relationships, either during the intervention itself, or since the last intervention session, whether at home or elsewhere. Items will include a modified 3-item version of the Conflict Tactics Scale to assess experience of emotional, physical, and sexual conflict since the last intervention session. Participants will be asked about the frequency of being the recipient of each type of conflict by their partner, as well as the perpetrator of each type of conflict. The questionnaire will also include an open-ended question to probe further on the occurrence of abuse if any is reported. The responses to this questionnaire will be reviewed immediately by the intervention facilitators, as well as a research assistant. Any indication of potential abuse or conflict resulting from the intervention, whether verbal or physical, will be reported immediately to the Investigators, and follow the plan for reporting adverse events (described below) and a protocol to minimize the risk of future adverse events, determine the safety of the participants' continued participation in the study, and refer the couple to support services (see "Protection of Human Subjects" section) for more details.

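### When only one partner reports conflict after a session, the only written referral is of the couple, which could reveal the report and its source

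*Combined protocol and SAP*

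**What the plan says.** The Monitoring Intimate Partner Violence (IPV) section sets out the pathway.

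- **Collection.** After each couples' session, "men and women will separately complete a brief questionnaire to collect process data on the feasibility and acceptability of the intervention". The same form carries a three-item conflict scale covering emotional, physical and sexual conflict since the last session.
- **Content.** Each person is asked how often they have experienced "being the recipient of each type of conflict by their partner, as well as the perpetrator of each type of conflict".
- **Trigger.** Facilitators and a research assistant look at the answers straight away. "Any indication of potential abuse or conflict resulting from the intervention, whether verbal or physical, will be reported immediately to the Investigators".
- **Action.** The case then follows the adverse-event plan and a protocol meant to limit further events, decide whether it is safe to continue, and "refer the couple to support services". For more detail the sentence points to a Protection of Human Subjects section. That heading is not in the Contents list or in the text available for review.

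The Process Data section describes the same post-session contact as including "questions to assess any unanticipated negative adverse events occurring because of the intervention (e.g., partner conflict", with no referral rule. The Data safety monitoring plan section lists "maintenance of the privacy and confidentiality of study subjects" among the general duties of investigators and staff.

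**The concern.** Asking the partners separately lets one of them disclose without the other knowing. That protection is only as good as the step that follows. Here the follow-up step names the couple as the unit of referral, and nothing in the section says what to do when only one partner has reported, or when the only report comes from the person who committed the act.

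If a partner who reported nothing is nevertheless referred for support, that person has reason to think the other one spoke. The measure intended to protect could then expose the reporter to the partner concerned. This harm is inferred from the wording; the documents neither describe nor measure it.

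**Working it through.** No formula applies, and the plan gives no figure to reproduce. The check reads the pathway in order and then looks for a rule elsewhere that would close the gap.

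**Step 1: can one partner disclose alone?** Yes. The questionnaires are completed separately, and each asks about both receiving and committing conflict.

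**Step 2: is one report enough to trigger action?** Yes, provided it indicates conflict resulting from the intervention. Agreement between the partners is not required.

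**Step 3: what referral follows?** The only one written is of the couple, whichever partner reported.

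| Who reported | Referral written | What the other partner could infer |
|---|---|---|
| Both | Couple | Each knows that they reported themselves; the referral need not point to the other |
| Only the person who experienced it | Couple | The person who committed the act is referred without having reported, so the other must have |
| Only the person who committed it | Couple | The affected partner is referred without having reported, so the other must have |

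The table lists situations and says nothing about how often each occurs.

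**Step 4: does it help if the two referrals are made privately?** Not fully. A partner who reported nothing and is referred, even alone, can still ask why. The inference comes from being referred at all.

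**Step 5: does another section supply the missing rule?**

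- *Process Data*: describes the questions and no referral.
- *Data safety monitoring plan*: a general privacy duty and no procedure.
- *Adverse events* and *Discontinuation/withdrawal*: reporting, review and stopping participation.
- *Training* sections: facilitators are trained to recognise and limit adverse outcomes, with no rule on one-sided reports.
- *Women found pregnant at baseline*: the research assistant "will inform the woman of the test results alone, unless the woman prefers for them to be delivered with her husband present", but the referral that follows is "a paper referral to the couples' preferred health facility". This is a precedent for private first disclosure and not for an individual referral.
- *Recruitment & Sampling*: when one partner declines the study, the interested person alone gets a family planning referral. This does not concern conflict, but it shows that the study can refer one partner alone.

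None of these gives an individual or confidential route to support services after a conflict report.

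**The case against.** The strongest reply is that the clause closes a one-sentence summary and is followed at once by a pointer to another section for detail. A summary should not be faulted for leaving out what it places elsewhere. This stands as a limit: the finding is that the available text writes no individual route. A reader might infer that the trial has no such safeguard at all; the documents do not support that, because the referenced section has not been seen.

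Second, naming the couple says who is to receive services. A reader might infer that the partners are referred together, in each other's presence, or told the reason. The text says none of this, and two private referrals would satisfy it. Nearby practice also leans towards separate handling: partners are screened apart where possible, and the baseline questionnaire requires privacy. This removes the stronger reading but not the point, for the reason in step 4.

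Third, the general privacy duty, immediate escalation to the investigators and facilitator training all weigh against a careless referral. They do, but none tells staff what to do with a one-sided report.

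Fourth, the trigger covers only conflict resulting from the intervention. That is correct, and it narrows the cases affected.

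**Conclusion.** The point holds in limited form. After a report from one partner only, the written referral could reveal that a report was made and by whom, and no available section prevents this. The severity is low to moderate: the possible harm is serious for the individual, but it is inferred from wording and may already be handled in the referenced section.

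The size of the risk cannot be estimated. The documents give neither a conflict rate nor the share of reports that are one-sided. A reader might take the two one-sided rows of the table as a probability of two in three; they are not, because the patterns need not be equally likely.

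The conclusion assumes that the couple referral is applied as written, including to the partner who did not report, and that the referenced section adds no individual route. Because the Data Analysis Plan is written in the past tense, the practical gain may lie mainly in any remaining or later use of this procedure.

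**What to change.** Replace the referral clause in the Monitoring Intimate Partner Violence (IPV) section with these rules:

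1. Support services are offered in private to the individual.
2. Staff never disclose one partner's answers to the other.
3. A joint referral is made only if the partner who experienced the conflict agrees. This applies even when both reported, because reporting is not consent to a joint referral. If both say they were on the receiving end, both must agree.
4. Every participant receives support-service information privately and routinely at the separate post-session questionnaire, whatever they answer. This reaches the affected partner when the only report comes from the perpetrator, without revealing that report.
5. An exception for imminent danger is stated, and the investigator's authority to discontinue participants is kept.

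Align the wording with the Protection of Human Subjects section. If that section already contains these rules, it is enough to say so explicitly in the IPV section.

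**Cost.** A few sentences of text, a check against the referenced section, and a short addition to the two-day research assistant training and the 5-day facilitator training. The post-session interview, planned at about 5 minutes, becomes slightly longer. Some couples will get no joint referral because the affected partner declines.

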#### Adverse events

The study is of minimal risk and therefore no serious anticipated adverse events are expected. Serious unanticipated events will be reported within 48 hours to the UTSA Human Investigation Committee and the Makerere IRB, the co-investigators listed on the protocol, and NICHD.

The joint-Principal Investigators (Drs. [name] and [name]) will conduct a review of all adverse events (serious and non-serious) every month during a scheduled meeting and keep a log of all events. They will evaluate the frequency and severity of the adverse event(s) and, in conjunction with the UTSA and Makerere IRBs, determine if modifications to the protocol or consent forms are required. A report to the three institution's IRB will be made when re-approval for the protocol is sought on a yearly basis, or more frequently if deemed necessary by the PIs based on the number and severity of adverse events. The summary will include the number of participants enrolled in the study and a summary of the adverse events to date (including relation to study and severity).

The joint-PIs, in conjunction with UTSA and Makerere IRBs, will be responsible for monitoring the data and conducting performance safety reviews at a minimum of every 3 months. The Principal Investigators, and the two institution's IRB, have the authority to stop or modify the study at any time. During the review process, the Principal Investigators will monitor and evaluate whether the study should continue unchanged, require modification, or close to enrollment.

## Discontinuation/withdrawal of participants from intervention

In this study, each participant has the right to withdraw from the trial at any time. In addition, the Investigator may discontinue a participant from the trial at any time if the Investigator considers it necessary for reasons such as; an adverse event that requires discontinuation of the intervention or results in inability to continue to comply with study procedures. The reason for withdrawal will be recorded in the Procedures for Recording Adverse Events (CRF).

#### Resource/Data Sharing Plan

Even though data sharing is not required since this project does not request >\$500,000 in any project year, we plan to share our data within our institutions. This project involves the collection of formative qualitative and quantitative baseline data in the first year and the collection of quantitative baseline data and data evaluating our intervention in year 2 in the Butambala Health sub-District of Uganda. In general, it is difficult to fully de-identify qualitative data and difficult to interpret without an understanding of the context. In addition, there will be Luganda terms in the text. As a result, we will not make these data available for data sharing. In addition, our intervention and control arm's data draws on medical record data that are the responsibility of the Butambala Health sub-district in Uganda. These data will only be available as included in the data set created from the quantitative assessments (baseline, follow-up assessments). These data will be made available under the following provisions:

- (1) The data will be fully de-identified
- (2) A period of three years elapses after the completion of the project to allow the PIs the opportunity to publish major findings
- (3) Access to the data will be limited to researchers and their students at the three collaborating institutions: Yale University, San Diego State University, and the Makerere University School of Public Health (MakSPH)

#### Other Permitted Access to Data

Direct access will be granted to authorised representatives from the Sponsor (NIH), host institutions and the regulatory authorities to permit trial-related monitoring, audits and inspections.

# Training of the RAs/Facilitators Training of research assistants

To collect baseline and follow-up interview data for the intervention experienced research assistants/interviewers will be hired for the purposes of the study. These individuals will be trained in the study procedures by one or more of the investigators. Research Assistants/interviewers will undergo a two-day training in the study procedures. They will also be actively involved in the piloting of training tools, which will serve as additional training. Throughout the duration of the study, the Investigators will monitor data collection procedures and the quality of data received, and conduct refresher trainings as needed. Clinic staff will also be oriented to the study and the study procedures by the investigators.

## Training of intervention facilitators

Group facilitators experienced in the delivery of behavioral interventions and health workers who will deliver the intervention will undergo a 5-day curriculum-based training of the intervention content using role playing and simulated group discussions led by [name] and [name]. Community leaders selected to facilitate session 3 discussions will participant in a 1-day training specific to their role. Training will emphasize the principles of voluntarism and informed choice with respect to contraceptive use, the role of gender equity in family planning, managing group dynamics, facilitating transformative dialogues without creating conflict, and identifying and minimizing adverse outcomes.

## Data Analysis Plan

We assessed baseline equivalence between the study arms on demographics using Generalized Estimating Equation (GEE) models in SPSS v. 28, which account for dependence from repeated, dyadic data. We tested intercorrelations between variables that differed (p < 0.10) between arms at baseline, or variables deemed theoretically relevant (i.e., age, number of children), to identify covariates. Based on these analyses, all models controlled for religion (based on differences in baseline equivalence) and age. The time by intervention interaction on contraceptive uptake (main outcome) at follow-up was tested using GEE with a logit link distribution (couple the unit of analysis). We report unintended pregnancy descriptively (underpowered but included for feasibility). For all secondary outcomes, GEE was used (linear for continuous outcomes and logistic for binary outcomes), with time and gender specified as within-subject effects. Unstandardized betas (b) and standard errors (SE) are reported for continuous outcomes and adjusted odds ratios (AORs) and 95% confidence intervals (CIs) are reported for binary outcomes.

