#### Inclusion criteria

- 1) Married or considers themselves married
- 2) Living with partner most of the time
- 3) Living within the selected villages in the last 3 months
- 4) Age 18 (or an emancipated minor) to 40 for women; age 18 to 50 for men
- 5) Luganda speaking
- 6) Not currently pregnant
- 7) Has no knowledge of infertility
- 8) Wanting to avoid pregnancy for at least a year (at least one person in the couple)
- 9) Not using a method of contraception at the moment OR only using low-efficacy or ineffective method of contraception (defined as using condom less than 100% of the time, Fertility-Awareness Based methods e.g., counting method, withdrawal method, spermicide, emergency contraception, and sponge)
- 10) Never used a non-reversible method (male or female sterilization)
- 11) Has sex in the past 3 months (woman)

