## Recruitment & Sampling

In each village, members of the Village Health Team (VHT) will assist our research staff in identifying potentially eligible couples. For the couples that we attempt to recruit based on the VHT's referral, the VHT will first independently visit couples' homes to introduce them to the study, and gain permission to return with the research assistant. If permission is granted, the VHT will accompany our research assistant to couples' homes to introduce our research assistant.

If both partners are together during this initial meeting, the research assistant will inform them of the overall study together, but will screen and assess eligibility separately, ensuring that participants are able to answer the eligibility screening questions about fertility preferences and current use of contraceptives in a private setting to ensure confidentiality. Research assistants will be trained in to try to separate spouses in a culturally appropriate and sensitive manner. In cases where the research assistant feels separate screening will not be possible, s/he will attempt to reschedule to come back and conduct the screenings separately. If a reschedule is not possible and screening must happen together, the research assistant will conduct a follow-up phone call or house visit with just the woman to confirm the accuracy of her responses. The research assistant will then obtain written informed consent from the participants. See recruitment script for eligibility screening questions. No identifying information will be collected for eligibility screening. The interviewer will proceed to conduct the baseline questionnaire after obtaining written informed consent for both partners.

If only one partner is present during the initial meeting, the research assistant will proceed with the eligibility screening. If the partner (male or female) is found eligible and interested, the research assistant will ask him/her to refer their partner to the study (either by calling their partner themselves, having the partner call the research assistant or the VHT). The research assistant will conduct the eligibility screening with the second partner over the phone, or will return to the house at the scheduled date and time, and follow the same procedures described above to assess eligibility, obtain informed consent for study participation, and conduct the baseline questionnaire.

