If an eligible participant is interested, but their partner declines participation, we will provide a referral to family planning services for a nearby clinic to the interested participant (in both the intervention and control villages to maintain balance between the study arms).

Enrolled couples can also refer other couples to the study (snowball sampling). They will provide the study contact to the referred couples directly, who can choose to contact the study team.

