#### Data collection

#### Questionnaires

**Baseline.** After the informed consent process in a one-on-one interview, using a computerized structured questionnaire in the participant's home or another agreed upon location, the Research Assistants will collect demographic information and the measures to assess family planning determinants. Participants can also complete the baseline interview over the phone shortly after enrollment if needed. Total duration ~45 minutes.

- **~7-month assessment**. Research Assistants will conduct a ~7-month follow up with the interviewers using an individual structured interviewer-administered computer-based interview (~45 minutes duration) in the participant's home, another agreed upon location, or via telephone. The 7-month questionnaire will serve as a measure of intervention effects on contraceptive use and relevant determinants of family planning. Total duration ~45 minutes.
- **~10-month assessment**. At ~10-month follow-up the interviewers will conduct an individual structured computer-based interview (~45 minutes duration) in the participant's home or another agreed upon location. Men and women may complete this survey via telephone; however, women must complete a second pregnancy test in-person. The 10-month questionnaire will serve as a measure of intervention effects on contraceptive use, contraceptive continuation, and relevant determinants of family planning. Total duration ~45 minutes (55 minutes for women taking pregnancy test)

\*Note: The study protocol originally planned for 3 and 6-month follow-up time points, but the assessment points were extended due to COVID-19 travel restrictions that occurred during the study.

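### If uptake means a method outside the eligibility list, the main-outcome interaction starts from an empty baseline and has no finite or stable value; an arm contrast at follow-up is needed

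*Combined protocol and SAP*

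**What the plan says.** The Data Analysis Plan gives the main outcome one sentence: "The time by intervention interaction on contraceptive uptake (main outcome) at follow-up was tested using GEE with a logit link distribution". Couples are the analysed units, SPSS v. 28 is named, and all models adjust for religion and age. Binary outcomes are to be reported as adjusted odds ratios with 95% confidence intervals.

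Inclusion criterion 9 admits two groups. One is "Not using a method of contraception at the moment". The other is "only using low-efficacy or ineffective method of contraception (defined as using condom less than 100% of the time", followed by fertility-awareness methods, withdrawal and several others.

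The Questionnaires section lists three assessments: baseline, ~7 months and ~10 months. It says of the first follow-up: "The 7-month questionnaire will serve as a measure of intervention effects on contraceptive use and relevant determinants of family planning". The ~10-month visit is given a similar role. The baseline interview need not coincide with screening: "Participants can also complete the baseline interview over the phone shortly after enrollment if needed".

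The document does not say whether uptake means any method or only one outside the criterion 9 list, how time is coded, or which contrast is primary. It gives no working correlation or convergence rule for the model.

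**The concern.** An arm-by-time interaction with baseline as a time level compares change from baseline between arms on the log-odds scale. That needs a baseline proportion away from zero. Criterion 9 may have removed it: if uptake means starting a method outside the list, nobody eligible has the outcome at entry, apart from a stray user picked up when the baseline interview follows enrolment.

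The stake is the interpretation of the main result. Under that reading the interaction may be non-estimable, may have almost no power, or may turn on one or two baseline records and on where the software stopped. Under the any-method reading the model works, but it counts a couple moving from a listed method to another method as unchanged. A reader cannot tell which case applies.

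**Working it through.** The document gives no sample size calculation, power or uptake rate, so there is no stated figure to reproduce. All rates below are assumptions.

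**Inputs.** 35 couples per arm: Process Data gives 70 intervention participants for exit interviews, read here as individuals, with an equal control arm assumed. Latent within-couple correlation 0.6, independence GEE, robust standard errors, no village effect, one baseline and two follow-ups; the interaction compares baseline with the pooled follow-ups.

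**Step 1: the algebra.** The interaction is

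[logit p(T, follow-up) − logit p(C, follow-up)] − [logit p(T, baseline) − logit p(C, baseline)].

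If both baseline proportions are 0, the second bracket is −∞ minus −∞ and is undefined. If exactly one is 0, the interaction is infinite.

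**Step 2: a few baseline users (hand example, treating visits as independent).** Follow-up 21/35 v 11/35:
- log odds ratio = ln[(21×24)/(14×11)] = 1.186
- variance = 1/21 + 1/14 + 1/11 + 1/24 = 0.252
- z = 1.186/0.502 = 2.36

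Now add baseline 3/35 v 1/35:
- baseline log odds ratio = ln[(3×34)/(32×1)] = 1.159
- variance = 1/3 + 1/32 + 1 + 1/34 = 1.394
- interaction = 1.186 − 1.159 = 0.026, odds ratio 1.03
- SE = √(0.252 + 1.394) = 1.283, z = 0.02

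Reverse the baseline counts (1/35 v 3/35) and the interaction odds ratio is 10.4 with z = 1.83. Four baseline records decide the estimate.

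**Step 3: zero baseline use, 60% v 35% at follow-up.** With a parameter-change rule of 1e-6, the interaction rejects in under 1% of trials and has no usable variance in 99.7%. At a fixed 20–30 scoring steps it also rejects under 1%. Stopped at 8–15 steps, it rejects in 59–60% of the same trials. The follow-up arm contrast rejects in 72%.

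**Step 4: 3% baseline use, no true effect (40% v 40%).** The probability that one arm has no baseline user is q = 0.97^35 = 0.344. Exactly one arm is empty with probability 2q(1−q) = 2 × 0.344 × 0.656 = 0.45.

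In such a trial the coefficient grows at each step, while the robust variance from the empty cell does not. Each couple there has score −μ and the cell's information is nμ(1−μ), so its contribution is nμ²/[nμ(1−μ)]² = 1/[n(1−μ)²], which tends to 1/35 = 0.029. In one simulated trial with a single stray user, the coefficient was −2.5 at 5 steps and −12.6 at 15, with robust SE 1.05 throughout, so the Wald ratio went from about −2.4 to −12.

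Stopped at 8–15 steps, the interaction therefore rejects in 45% of null trials. At 25–30 steps it rejects in 1–2%. With the 1e-6 rule, 45% of trials have no usable variance. The follow-up contrast rejects in 4%. By the same formula, the one-empty-arm probability at 1, 3 and 5% baseline use is 42, 45 and 28% with 35 couples per arm, and 50, 21 and 5% with 70.

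**Step 5: any method counts, 30% baseline use.** The interaction has 5% false positives, so it is valid. For 60% v 35% its power is 53%, against 69% for the unadjusted follow-up contrast and about 76% for the contrast adjusted for baseline use.

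On switching, suppose 30% use a low-efficacy method and non-switchers keep it. Effective-method uptake of 60% v 35% has odds ratio (0.60/0.40)/(0.35/0.65) = 2.79. Any-method use becomes 0.60 + 0.40×0.30 = 72% v 0.35 + 0.65×0.30 = 54.5%, odds ratio 2.15.

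**The case against.** **Uptake may mean any method.** Criterion 9 lets in low-efficacy users, the Questionnaires section speaks of contraceptive use without restriction, and the plan promises odds ratios, which an all-zero baseline could not supply for the interaction. This stands: the near-zero baseline is conditional on a definition that the document does not give.

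**The false-positive rate depends on early stopping.** This also stands. A reader might infer from the 45% figure that the reported result is likely to be spurious. The documents do not support that. The rate needs about 3% baseline use and a stop at about 8–15 steps, and no iteration rule is given. A second GEE routine at its defaults rejected 0% (Step 3 setting) and 4% (Step 4 setting), with 54% and 21% of fits unusable. Failure or lack of power is the better-supported harm.

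**The visits are listed.** Correct. Three assessments is the natural reading; only the time coding and the primary contrast are missing.

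**The interaction is not always weaker.** Also correct. With any method counted and correlation 0.8, it had 64% power against 62% for an unadjusted follow-up contrast.

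**Couple-level rules are matters of choice.** The document does not say how discordant partner reports, clinic records or pregnancy at follow-up were handled. A reader might infer that particular rules are needed, such as taking the woman's report. The document confirms answers with the woman alone only when joint screening could not be avoided, and only for eligibility. The rules should be disclosed; none is required here.

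**Conclusion.** The concern holds conditionally. The certain part is that uptake, the time coding and the primary contrast are not stated, and that criterion 9 excludes current users of any method outside its list. If uptake means such a method, the interaction has no finite or stable value. Under the assumed inputs it is unusable or almost never rejects when iterated to convergence, against about 70% power for the follow-up contrast. A false positive is possible only with a near-zero baseline and early stopping. If uptake means any method, the test is valid, but the effect is diluted by unscored switching (odds ratio 2.79 to 2.15 in the example).

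A reader might go further and call the interaction invalid outright, or the trial's result wrong. Neither follows. The definition used, the baseline counts and the convergence status are unknown, and the sample size is assumed. This should be fixed; confidence is medium because the harm depends on the definition.

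**What to change.** 1. State the uptake definition that was used and give baseline uptake counts by arm. State, as applied, the rules for discordant partner reports, clinic records and pregnancy.
2. Report the arm effect at follow-up, at each visit and averaged over the ~7- and ~10-month visits, from a GEE with arm, visit, baseline low-efficacy use, religion and age, labelled post hoc. If baseline uptake is zero or near zero, base the main-outcome conclusion on this contrast. Otherwise keep the interaction and report the contrast beside it.
3. For the fitted interaction, state the time coding, the type of standard error and whether the model converged.
4. Show the follow-up contrast with an allowance for village alongside the couple-level result, because the arms consist of villages: referrals are offered "in both the intervention and control villages to maintain balance between the study arms".

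**Cost.** One added model, a table of counts and some wording. The data exist if the questionnaires recorded method type. The analysis section is in the past tense, so the contrast is post hoc.

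Village is the harder cost. With an assumed 2 or 4 villages per arm and latent ICC 0.02–0.05, couple-level standard errors give the follow-up contrast 7–13% false positives. The design effect 1 + (35/K − 1)×ICC runs from 1 + 7.75×0.02 = 1.16 (K = 4) to 1 + 16.5×0.05 = 1.83 (K = 2), with 2K − 2 = 6 or 2 degrees of freedom. The couple-level interval is then too narrow and the village-level one wide, so both should be shown.
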